9.2.2.3 Simplified Disease Activity Index Score

The Simplified Disease Activity Index (SDAI) score is a derived score combining tender joints (28 joints), swollen joints (28 joints), GH, Physician’s global assessments of disease activity (PGH), and CRP.²

SDAI is defined as follows:

SDAI = TEN28 + SW28 + GH + PGH + CRP (mg/dL) where:

- TEN28 and SW28 were defined the same as in Section [9.2.2.2.1](#)
- GH is Patient’s Global Assessment of Disease Activity on VAS.
- PGH is Physician’s Global Assessment of Disease Activity on VAS.

9.2.2.4 Clinical Disease Activity Index Score

Clinical Disease Activity Index (CDAI) score is a derived score combining tender joints (28 joints), swollen joints (28 joints), GH, and PGH.²

CDAI is defined as follows:

CDAI = TEN28 + SW28 + GH + PGH where:

CNTO 136 (sirukumab): Clinical Protocol CNTO136ARA3004 – Amendment 3

- TEN28 and SW28 were defined the same as in Section 9.2.2.2.1
- GH is Patient’s Global Assessment of Disease Activity on VAS.
- PGH is Physician’s Global Assessment of Disease Activity on VAS.

Note: CDAI is the same as SDAI, except that CRP is not included.

9.2.2.5 ACR/EULAR Remission

9.2.2.5.1 SDAI-Based ACR/EULAR Remission

SDAI-based ACR/EULAR remission is defined as a SDAI value of ≤ 3.3 at a visit¹⁰:

9.2.2.5.2 Boolean-Based ACR/EULAR Remission

A subject is considered as having achieved the Boolean-based ACR/EULAR remission at a visit if he/she meets all of the following 4 criteria at that visit¹⁰:

- Tender joint count (68 joints) ≤ 1 .
- Swollen joint count (66 joints) ≤ 1 .
- CRP ≤ 1 mg/dL
- Patient’s Global Assessment of Disease Activity on VAS ≤ 1 on a 0 to 10 scale.

9.2.3 Endpoints

Primary Endpoint

The primary endpoint is the number of subjects with each of the following long-term safety events through the end of the study: cardiovascular SAEs, malignancies, serious infections, and gastrointestinal perforations.

Major Secondary Endpoints

Laboratory parameters of interest (neutrophils, platelets, hepatobiliary parameters, and lipid parameters) will be observed.

Other secondary endpoints

- ACR responses
- DAS28
- HAQ-DI
- SF-36
- WLQ
- HECONQ
- Morning stiffness

9.3 Pharmacokinetics and Immunogenicity

9.3.1 Evaluations

Serum samples will be used to evaluate the pharmacokinetics, as well as the immunogenicity of sirukumab (antibodies to sirukumab). Serum collected for sirukumab serum concentration and antibodies to sirukumab analyses may additionally be used to evaluate safety or efficacy aspects that address concerns arising during or after the study period. Genetic analyses will not be performed on these serum samples. Subject confidentiality will be maintained. At visits where sirukumab serum concentration and antibodies to sirukumab will be evaluated, 1 blood draw of sufficient volume can be used. Venous blood samples will be collected and each serum sample will be divided into 3 aliquots (1 each for pharmacokinetics, antibodies to study agent, and a back-up). Subjects who discontinue study participation should have serum samples collected at the last safety follow-up visit.

Instructions for the collection, handling, and shipment of these samples are found in the Laboratory Manual.

9.3.2 Pharmacokinetics

9.3.2.1 Serum Collection and Handling

Blood samples for the measurement of serum sirukumab concentrations will be collected at visits as shown in the Time and Events Schedules ([Table 1](#) and [Table 2](#)). For subjects who had serum samples collected at earlier time points in study CNTO136ARA3002 (approximately 750 randomized subjects in CNTO136ARA3002) and all subjects who enrolled after participating in study CNTO136ARA3003, serum samples will be collected at Weeks 2, 4, 16, 28, 52, 104, 156 and the final safety and efficacy follow-up visit ([Table 1](#) and [Table 2](#)). One additional sample will be collected at Week 208 for subjects who enrolled after participating in study CNTO136ARA3003.

The exact dates and times of blood sampling must be recorded on the laboratory requisition form. Note that if the subject is to receive an administration of study agent at that visit, blood samples will be collected prior to study agent administration.

9.3.2.2 Analytical Procedures

Serum samples will be analyzed to determine concentrations of sirukumab using a validated, immunoassay method.

The Sponsor, or its designee, under conditions in which the subjects' identity remains blinded, will assay these samples.

9.3.2.3 Pharmacokinetic Parameters

Serum sirukumab concentration including C_{trough} will be summarized.

9.3.3 Immunogenicity Assessment (Antibodies to sirukumab)

To assess the immunogenicity of sirukumab, serum samples for the detection of antibodies to sirukumab will be collected at visits as shown in the Time and Events Schedules ([Table 1](#) and [Table 2](#)). For subjects who had serum samples collected at earlier time points in study

CNTO 136 (sirukumab): Clinical Protocol CNTO136ARA3004 – Amendment 3

CNTO136ARA3002 (approximately 750 randomized subjects in CNTO136ARA3002) and all subjects who enrolled after participating in study CNTO136ARA3003, serum samples will be collected at Weeks 16, 28, 52, 104, 156 and the final safety and efficacy follow-up visit. One additional sample will be collected at Week 208 for subjects who enrolled after participating in study CNTO136ARA3003.

Antibodies to sirukumab will be detected using a validated immunoassay method. Serum samples will be screened for antibodies binding to sirukumab and the titer of confirmed positive samples will be reported. Other analyses may be performed to verify the stability of antibodies to sirukumab and/or further characterize the immunogenicity of sirukumab. These samples will be analyzed by the Sponsor or its designee.

Subjects will be classified as positive for antibodies to sirukumab if any post-treatment samples tested positive for antibodies to sirukumab. Subjects will be classified as negative for antibodies to sirukumab if antibodies were not detected in any post-treatment samples.

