The number of subjects with each of the following long-term safety events: cardiovascular SAEs, malignancies, serious infections, and gastrointestinal perforations will be summarized. Serious cardiovascular events adjudicated by the CEC will be summarized by treatment group. No hypothesis testing will be performed.

- **Secondary Analyses**

The laboratory parameters of interest (neutrophils, platelets, hepatobiliary parameters, and lipid parameters) will be summarized by the treatment group over time. Baseline value is defined as the baseline value of study CNTO136ARA3002 or CNTO136ARA3003, respectively.

- **Other Planned Analyses**

- **Safety Analyses**

Additional analyses will be performed for the number of patients with cardiovascular SAEs by cardiovascular type and the number of patients with malignancies by malignancy type (eg, lymphoma, nonmelanoma skin cancers, other malignancies).

Other safety data will be assessed by summarizing the proportion of subjects with AEs, the types of AEs, infections, SAEs, AEs leading to discontinuation, and changes in laboratory parameters.

- **Efficacy Analysis**

The following efficacy endpoints will be summarized by treatment group over time:

- ACR responses
- DAS28
- HAQ-DI
- SF-36

Baseline value in efficacy is defined as the baseline value of study CNTO136ARA3002 or CNTO136ARA3003. No missing data imputation will be used.

- **Medical Resource Usage and Health Economics**

WLQ and HECONQ data will be summarized over time.

- **Pharmacokinetic and Immunogenicity Analyses**

CNTO 136 (sirukumab): Clinical Protocol CNTO136ARA3004 – Amendment 3

Serum sirukumab concentration data including C_{trough} will be summarized. PK data may be displayed graphically. If sufficient samples are collected, steady-state trough serum sirukumab concentrations before and after switching from PFS-U to PFS-AI will be evaluated.

The incidence of antibodies to sirukumab will be summarized for subjects with appropriate samples for detection of antibodies to sirukumab (ie, at least 1 sample obtained after sirukumab administration).

- **Pharmacodynamic Analyses**

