11.2 Efficacy and Safety Analyses

Baseline value in efficacy and safety is defined as the baseline value of study CNTO136ARA3002 or CNTO136ARA3003. No missing data imputation will be used.

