11.4 Immunogenicity Analyses

The incidence of antibodies to sirukumab will be summarized for all subjects who have appropriate samples. Additional analysis may be performed as needed.

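### The antibody rule in Protocol 9.3.3 ignores pre-dose results, so pre-existing reactivity that persists after treatment is counted as incidence of antibodies to sirukumab

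*Protocol*

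**What the plan says.** Protocol Section 9.3.3 gives a two-sided classification. For positives: "Subjects will be classified as positive for antibodies to sirukumab if any post-treatment samples tested positive for antibodies to sirukumab". For negatives: "Subjects will be classified as negative for antibodies to sirukumab if antibodies were not detected in any post-treatment samples".

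The synopsis (Pharmacokinetic and Immunogenicity Analyses) makes a subject evaluable with "at least 1 sample obtained after sirukumab administration". Section 11.4 defines the summary: "The incidence of antibodies to sirukumab will be summarized for all subjects who have appropriate samples".

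On timing, Section 9.3.3 says "serum samples will be collected at Weeks 16, 28, 52, 104, 156 and the final safety and efficacy follow-up visit", with Week 208 added for subjects who came from CNTO136ARA3003. Table 1 agrees: antibody sampling starts at Week 16 and there is no Week 0 sample. All subjects from CNTO136ARA3003 are sampled. From CNTO136ARA3002, only those already sampled in that study are included ("approximately 750 randomized subjects in CNTO136ARA3002").

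Titers are available: "Serum samples will be screened for antibodies binding to sirukumab and the titer of confirmed positive samples will be reported". The classification does not use them.

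**The concern.** Incidence describes new cases. A reader of the study report will take an incidence of antibodies to sirukumab as the rate at which the drug provokes antibodies. The stated rule measures something else: the share of subjects with any positive sample after treatment. Some sera may react in the assay before any exposure. Where such a subject also tests positive later, the rule cannot separate that result from a response to the drug.

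Immunogenicity is a named secondary objective (Section 2.1). The error can only run upward, and it is proportionally largest when the true rate is low. The stakes are limited to how this descriptive result is read. No hypothesis test, sample size or primary endpoint depends on antibody status, and neither do the discontinuation and interruption rules in Sections 10.2 and 10.2.1.

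**Working it through.** **Plan's own figure.** There is none to reproduce. The documents state no antibody rate, baseline or later.

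**Step 1: apply the rule to each kind of subject.**

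| Before first dose | After treatment | Status under 9.3.3 | Treatment-emergent? |
|---|---|---|---|
| Negative | Negative throughout | Negative | No |
| Negative | Positive at least once | Positive | Yes |
| Reactive | Negative throughout | Negative | No |
| Reactive | Positive, no titer rise | Positive | No |
| Reactive | Positive, titer rise | Positive | Yes (boosted) |

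Only the fourth row is misplaced. The third row shows that a pre-dose reactor is not always counted.

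**Step 2: look for a baseline elsewhere.** Section 11.2 says: "Baseline value in efficacy and safety is defined as the baseline value of study CNTO136ARA3002 or CNTO136ARA3003". Sections 11.5, 11.6 and 11.7 tie pharmacodynamic, methylation and health-economics results to the parent-study baseline. Section 11.4 has no such link. Because the first antibody sample in this extension is at Week 16, any pre-dose result must come from the parent study.

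**Step 3: size.** All three inputs are assumptions:
- b = share reactive before the first dose
- s = share of those positive later without a titer rise
- i = treatment-induced rate among subjects negative at baseline

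Rate under the rule = (1 − b) × i + b × s

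Treatment-emergent rate = (1 − b) × i

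Excess = b × s

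Boosted subjects would add the same amount to both rates, so they leave the excess unchanged. They are set to zero here.

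| b | s | i | Under the rule | Treatment-emergent | Excess (points) |
|---|---|---|---|---|---|
| 1% | 0 | 2% | 1.98% | 1.98% | 0 |
| 1% | 0.5 | 2% | 2.48% | 1.98% | 0.5 |
| 1% | 1 | 2% | 2.98% | 1.98% | 1.0 |
| 3% | 0.5 | 2% | 3.44% | 1.94% | 1.5 |
| 3% | 1 | 2% | 4.94% | 1.94% | 3.0 |
| 1% | 1 | 5% | 5.95% | 4.95% | 1.0 |
| 3% | 1 | 5% | 7.85% | 4.85% | 3.0 |

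For example, the fifth row is 0.97 × 0.02 + 0.03 × 1 = 0.0494, against 0.97 × 0.02 = 0.0194.

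**Step 4: in subjects.** If all of the roughly 750 sampled subjects from CNTO136ARA3002 entered and were evaluable, the ceiling for that cohort over this range is 750 × 0.03 × 1 = 22.5. The 750 counts subjects randomized in the parent study, not those entering the extension, so this is for scale only.

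**The case against.** The strongest reply is that the protocol never claims treatment-emergent incidence. Any positivity during long-term exposure is a legitimate summary, and titers of confirmed positives are reported. Sections 9.3.3 and 11.4 both leave room for further analyses. Section 11 promises a separate SAP for integrating parent-study and extension data, including immunogenicity. A baseline-adjusted definition could stand there or in this study's SAP, whose text was not available to this review.

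Much of this stands as a limit on the point. The summary itself is legitimate; the fault is the label and the absence of a companion measure. The further analyses are optional and unspecified, and they do not alter the classification. If a SAP does define status against baseline, the protocol rule still has to be reconciled with it.

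Three stronger readings are tempting, and the documents do not support them:

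- A reader might infer that every subject reactive before treatment is counted. That is not so: a subject negative in all later samples is classified negative.
- A reader might infer that the reported figure must be some multiple of the true one. With b of 1% to 3%, i of 2% to 5% and full persistence (s = 1), the ratio of the two rates runs from 5.95/4.95 = 1.20 to 4.94/1.94 = 2.55. At s = 0.5 it runs from 5.45/4.95 = 1.10 to 3.44/1.94 = 1.77. At s = 0 or b = 0 it is 1.0. Nothing in the documents fixes s or b.
- A reader might infer that links between antibody status and trough level, response or hypersensitivity are diluted. No such analysis is specified. Section 11.3 summarizes concentrations by visit, and the planned association with clinical response in Section 11.5 concerns biomarkers.

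**Conclusion.** The point holds for the protocol text. The classification is complete as written, uses only samples after treatment, and is reported as incidence. It therefore includes pre-existing reactivity that persists. This is a stated rule with a better alternative, not a missing laboratory detail.

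The direction is certain wherever pre-existing reactivity exists and persists. The size is unknown: b × s, or 0 to 3 percentage points for assumed b of 1% to 3% and s of 0 to 1, and possibly nil. It does not follow that the plan as a whole will report a wrong figure, because the SAP could not be checked. The change is worth making for a secondary objective, but it does not affect the primary safety analysis.

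**What to change.** In Sections 9.3.3 and 11.4, and in the matching synopsis text:

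1. Keep the present count, labelled as any positive sample after treatment.
2. Add treatment-emergent incidence: negative before the first sirukumab dose in the parent study and positive later, or a titer rise over the pre-dose titer by a margin fixed in advance from assay validation.
3. Show pre-existing positives, and subjects with no pre-dose result, as separate rows.
4. Reconcile this wording with any antibody definition in the SAP and the integration SAP.

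The cost is revised wording and a merge with parent-study antibody results. The treatment-emergent analysis will have a smaller evaluable set if some subjects lack a pre-dose sample. Whether those samples exist has to be confirmed first: the documents mention only earlier time points for the CNTO136ARA3002 cohort and describe no parent-study antibody schedule for CNTO136ARA3003. If they exist, no new sampling is needed. Where they do not, the affected subjects go in the no-pre-dose row.

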- f. Urine pregnancy testing during the study for women of childbearing potential only. Additional pregnancy tests may be performed, as determined necessary by the investigator or required by local regulation, to establish the absence of pregnancy at any time during the subject's participation in the study.
- g. RA assessments include the following: patient pain assessment; patient global assessment of disease activity, physician global assessment of disease activity, Health Assessment Questionnaire-Disability Index, and duration of morning stiffness.
- h. At selected sites, the MPSQ will be administered as an optional paper questionnaire to subjects who consent to participate after implementation of Amendment 3 at the study site.
- i. Pharm serum samples (sirukumab concentration and antibodies to sirukumab) will be collected from subjects who had pharm serum samples collected at earlier time points in study CNTO136ARA3002 (approximately 750 subjects randomized in CNTO136ARA3002 before 18 November 2013) and from all subjects enrolled after participating in study CNTO136ARA3003.
- j. On days of study agent administration, Pharm serum samples (sirukumab concentration and antibodies to sirukumab) must be collected prior to administration. Blood collected from one venipuncture will be divided into 3 serum aliquots (1 each sirukumab concentration, antibodies to sirukumab and a backup sample). Refer to the Central Laboratory Manual for more detailed instructions.
- k. Pharm serum samples (sirukumab concentration and antibodies to sirukumab) will be collected only from those subjects who enrolled after participating in study CNTO136ARA3003.
- l. An optional pharmacogenetics blood sample will be collected from those subjects who sign a separate consent form (where local regulations permit).

CNTO 136 (sirukumab): Clinical Protocol CNTO136ARA3004 – Amendment 3

Table 2: Times and Events in Safety and Efficacy Follow-up After Last Study Agent Injection or after Discontinuation of Study Agent				
	Week 4	Week 8	Week 12	Week 16/Final Safety and Efficacy Follow-up Visit
Study Procedure ^{a,b}				
Safety Assessments				
Blood pressure	X	X	X	X
Efficacy Assessments				
Patient pain assessment		X		X
Patient global assessment of disease		X		X
Physician global assessment of disease		X		X
Clinical Laboratory Assessments				
Hematology panel		X		X
Chemistry panel		X		X
Lipid panel (fasting)		X		X
CRP		X		X
Pharmacokinetics/ Immunogenicity				

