3.2.3 Study Phases and Duration of Treatment

There will be 3 phases of this LTE study: Blinded active treatment, open-label treatment, and safety and efficacy follow-up.

CNTO 136 (sirukumab): Clinical Protocol CNTO136ARA3004 – Amendment 3

As described in Section 3.2.2, the blinded active treatment phase will continue until following 3 conditions have been met: the Week 52 DBL occurs in study CNTO136ARA3002, the Week 24 DBL occurs in study CNTO136ARA3003, and the last AI usability substudy subject completes the Week 16 visit or terminates from the study.

The open-label treatment phase of the study will begin after those 3 conditions have been met, and will continue through the last scheduled dose for all subjects. The safety and efficacy follow-up will include approximately 16 weeks of study evaluations following the last administration of study agent, including follow-up for patients who discontinued study treatment prior to their last scheduled dose. The safety and efficacy follow-up allows for monitoring of the subject for a period of equivalent to at least 5 times the half-life of sirukumab.

The maximum duration of the study is expected to be 156 weeks for subjects enrolling after participation in study CNTO136ARA3002 and 208 weeks for subjects enrolling after participation in study CNTO136ARA3003, followed by approximately 16 weeks of safety and efficacy follow-up after the administration of the final study agent injection of sirukumab.

After a minimum of 1 year treatment in CNTO136ARA3004 for subjects from study CNTO136ARA3002, or a minimum of 2 years of treatment in CNTO136ARA3004 for subjects from CNTO136ARA3003, and after sirukumab is approved for the treatment of RA in the subject's country of residence, the Sponsor may no longer offer study treatment in CNTO136ARA3004 for those specific subjects. At that point the subject will have the opportunity to discuss treatment options with their treating physician.

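### The antibody-negative rule ignores drug level, so if the assay does not tolerate on-treatment troughs, masked antibodies would count as negative in subjects without the washout sample

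*Protocol*

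**What the plan says.** Section 9.3.3 of the protocol gives both halves of the classification. For positives: "Subjects will be classified as positive for antibodies to sirukumab if any post-treatment samples tested positive for antibodies to sirukumab". For negatives: "Subjects will be classified as negative for antibodies to sirukumab if antibodies were not detected in any post-treatment samples". There is no third class and no condition on drug concentration. The assay is described only as a validated immunoassay, without a drug-tolerance limit.

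On timing, the same section states that "serum samples will be collected at Weeks 16, 28, 52, 104, 156 and the final safety and efficacy follow-up visit", with a Week 208 sample added for subjects from CNTO136ARA3003. Table 1, footnote j, adds that on dosing days these samples "must be collected prior to administration". It also says "Blood collected from one venipuncture will be divided into 3 serum aliquots", one for sirukumab concentration, one for antibodies and one as backup. Table 2 (footnotes c and d) applies the same split to the final follow-up visit.

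The Synopsis (Pharmacokinetic and Immunogenicity Analyses) describes the evaluable subject as one with appropriate samples, "ie, at least 1 sample obtained after sirukumab administration". Section 11.4 summarises incidence over subjects with appropriate samples and leaves further analysis optional. Section 3.2.3 describes the 16-week follow-up as allowing "monitoring of the subject for a period of equivalent to at least 5 times the half-life of sirukumab".

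**The concern.** Circulating drug can hide antibodies from an immunoassay. A result of no antibody detected is informative only when the drug level in that sample is within what the assay tolerates. Above that level the result is inconclusive, yet section 9.3.3 counts both kinds as negative.

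Immunogenicity is a stated secondary objective, and results are shown by dose group. If masking occurs, incidence would be understated in subjects whose only samples were drawn on treatment, and more so in the group with higher troughs. Sections 1.2 and 3.2.2 report more hypersensitivity and injection-site reactions at 100 mg q2 weeks. A falsely low antibody rate at that dose would make those findings harder to interpret.

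**Working it through.** The plan states no antibody incidence, tolerance limit or sample size for this objective, so there is no figure to reproduce. The checks below concern direction and possible size.

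**1. Half-life bound.** Follow-up is 16 weeks, or 112 days, and section 3.2.3 says this covers at least 5 half-lives. So the half-life is at most 112/5 = 22.4 days (3.2 weeks). The documents give no lower bound; 14 days is used here as an assumption.

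**2. Trough ratio between groups.** Assume linear one-compartment kinetics at steady state. The trough is proportional to D·r/(1 − r), with r = 2^(−τ/t½). For 100 mg every 2 weeks against 50 mg every 4 weeks this reduces to

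ratio = 2 × (1 + 2^(2/t½)), with t½ in weeks.

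- t½ = 3.2 weeks: 2 × (1 + 1.542) = 5.1
- t½ = 2.5 weeks: 2 × (1 + 1.741) = 5.5
- t½ = 2.0 weeks: 2 × (1 + 2) = 6.0

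A shorter half-life gives a larger ratio, so under this model the ratio is at least about 5.

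**3. What the follow-up sample achieves.** After 5 half-lives, 2^(−5) = 3.1% of the post-dose level remains. Relative to each group's own trough at t½ = 3.2 weeks:

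- 100 mg q2 weeks: 2^(−14/3.2) = 4.8%
- 50 mg q4 weeks: 2^(−12/3.2) = 7.4%

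At t½ = 2.0 weeks these fall to 0.8% and 1.6%. The follow-up sample is therefore much less exposed to masking, and it enters the same any-sample rule.

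**4. Who lacks that sample.**

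- Section 10.3 lists loss to follow-up, withdrawal of consent and death as ways to leave the study.
- Section 9.3.1 says only that subjects who discontinue participation should have serum collected at the last safety follow-up visit.
- Sections 11 and 11.9 foresee integrated immunogenicity analyses at interim releases or locks. A subject still on treatment then has no washout sample in this study. The parent study supplies none either, because its last dose is Week 0 here (section 6.1).

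Any of these subjects with one on-treatment sample is evaluable and can be classed negative.

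**5. Illustration of size.** None of these inputs is in the documents. Assume true incidence 5% in both groups, a fraction m of antibody-positive subjects masked on treatment, a fraction f who give a washout sample, and every masked case found at washout. Then observed incidence = 5% × (1 − m × (1 − f)).

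| f | m = 0.1 (50 mg) / 0.3 (100 mg) | m = 0.5 (50 mg) / 0.9 (100 mg) |
|---|---|---|
| 0 (all still on treatment) | 4.50% / 3.50% | 2.50% / 0.50% |
| 0.5 | 4.75% / 4.25% | 3.75% / 2.75% |
| 0.9 | 4.95% / 4.85% | 4.75% / 4.55% |
| 1.0 | 5.00% / 5.00% | 5.00% / 5.00% |

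With no masking (m = 0) every cell is 5.00%. The effect is small when nearly everyone gives the washout sample and can be large at an interim lock.

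**6. Check on an obvious remedy.** Dropping inconclusive subjects and dividing by positives plus confirmed negatives is also biased. Take 1000 subjects, 50 truly positive and all detected on treatment, with 60% giving a washout sample and on-treatment negatives treated as invalid. Confirmed negatives are 950 × 0.6 = 570, so incidence is 50/(50 + 570) = 8.1% against a true 5.0%.

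**The case against.** The design already contains the usual safeguard. A sample after at least 5 half-lives is scheduled for the whole sampled population, including those who stop drug early and enter the Table 2 follow-up. One positive result there makes the subject positive. The assay is validated and may tolerate the 100 mg troughs, in which case nothing is lost. The analysis is descriptive, without hypothesis tests, and the groups are not randomised in this study. Group 1 subjects may also switch to 50 mg q4 weeks (section 5.1), which moves their later samples toward Group 2 troughs. Sections 9.3.3 and 11.4 allow further immunogenicity analyses. A separate SAP for integration is promised, and the SAP text available here carries no analysis content, so a drug-level rule elsewhere cannot be excluded.

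Much of this stands, and it rules out stronger readings. A reader might infer that masked antibodies are in fact being counted as negative, or that incidence is biased low throughout. The documents do not support that: tolerance is not given, and the follow-up sample can recover masked cases. A reader might also infer that a lower rate at 100 mg would have to be an assay artefact. That rests on the unknown tolerance and an assumed kinetic model. Nor are the concentrations unused: section 11.3 summarises them, but nothing links them to antibody status.

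What the objection does not reach is the subject without a washout sample, or whose antibodies have gone by then. For these the protocol's rule makes no check on drug level, and the further analyses it allows are optional.

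**Conclusion.** The point holds conditionally. Section 9.3.3 treats a negative drawn at a high drug level the same as a drug-free negative, and the evaluability rule does not require a washout sample. If tolerance lies below on-treatment troughs, masked antibodies would be counted as negative in subjects without the final follow-up sample, most of all at an interim lock. If tolerance lies between the two groups' troughs, the problem falls mainly on 100 mg q2 weeks. The 5- to 6-fold trough ratio depends on linear one-compartment kinetics and a half-life of 14 to 22.4 days.

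The number of subjects reclassified cannot be computed from the documents. Because the objective is secondary and descriptive, this is a change worth making rather than a threat to the study's main conclusions.

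The term post-treatment is also ambiguous. The Synopsis points to any sample after dosing, while section 9.1.4 uses Posttreatment Phase for follow-up only.

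**What to change.** Amend sections 9.3.3 and 11.4, and carry the same wording into the SAP and the integration SAP:

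- State the assay's validated drug-tolerance limit and define a post-treatment sample.
- Use the paired concentration to label as *negative, inconclusive* any subject with no positive sample and no sample below that limit.
- Keep all subjects with appropriate samples as the denominator of the main incidence, and describe it as a lower bound.
- Show the inconclusive count by dose group and by dose at the time of sampling, because of the 100 mg to 50 mg switch.
- Report separately the incidence in the final follow-up sample, among subjects who gave it with a concentration below the limit.
- Do not use positives plus confirmed negatives alone as the denominator, because that inflates incidence when washout samples are missing.

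The cost is wording and one or two extra table columns, since the paired samples are already scheduled. The downside is a less definite stated incidence. If the assay tolerates the 100 mg troughs, results do not change and the report will show that.
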